9.7.1.8.4 VITAL SIGNS

Descriptive statistics for vital signs parameters (ie, systolic and diastolic BP, pulse, respiratory rate, temperature, weight), and changes from baseline will be presented by visit and treatment group.

9.7.1.8.5 ELECTROCARDIOGRAMS

Descriptive statistics for ECG parameters and changes from baseline will be presented by visit and treatment group. Shift tables will present changes from baseline in ECG interpretation (categorized as normal; abnormal, not clinically significant; and abnormal, clinically significant) to the end of treatment.

In addition, the number (percentage) of subjects with at least 1 postbaseline abnormal ECG result in QTcF during the treatment period will be summarized. Clinically abnormal ECG results in QTcF will be categorized as follows:

Absolute QTc interval prolongation:

- QTc interval >450 msec
- QTc interval >480 msec
- QTc interval >500 msec

Change from baseline in QTc interval:

- QTc interval increases from baseline >30 msec
- QTc interval increases from baseline >60 msec

9.7.1.8.6 OTHER SAFETY ANALYSES

Cognitive decline will be assessed as a safety assessment, in addition to efficacy assessments. Cognitive assessments will include the ADAS-cog₁₄, MMSE, CDR, and CBB (see [Section 9.7.1.6](#)).

9.7.2 Determination of Sample Size

9.7.2.1 Sample Size Rationale in the MCI/Prodromal Cohort

Primary endpoint – derived ADCOMS

The sample size and design characteristics to test the hypothesis for the primary objective based on the primary endpoint, change from baseline of the derived ADCOMS at 18 months, were determined by means of simulations. Extensive study simulations have shown that a total of 500 subjects will be sufficient to demonstrate that the most likely ED₉₀ dose achieves a 25% improvement over placebo with a probability of at least 80% in the interim and final analyses. There is at least a 90% probability of study success for the dose response scenarios

where treatment was considered to have a clinically meaningful treatment effect. Simulations have also shown that if there is no obvious dose effect, the probability of falsely claiming superiority to placebo is at most 5%.

For each of the 4 treatment groups (3 active doses and placebo) the final number of subjects per group will differ depending on the observed interim treatment responses. The simulation plan will be an appendix to the statistical analysis plan and will present further details.

vMRI

The null hypothesis is that there is no difference between active dose and placebo. There are 3 null hypotheses corresponding to 3 active doses. The alternative hypothesis is that at least 1 null hypothesis is false (1-sided). The null hypotheses will be tested using Dunnett's method with 1-sided alpha of 0.05. The statistical power was estimated through simulation for a moderate dose-response assumption that the percent reduction in change from baseline of total hippocampal volume compared with placebo would be 15%, 20%, and 25% corresponding to the 3 doses, respectively. The estimated power for the actual planned study sample size is 78% at 18 months assuming an attrition rate of 20% at 18 months. Under a stronger dose-response assumption (ie, the percent reduction in change from baseline of total hippocampal volume compared with placebo is twice as much as that in the moderate dose-response assumption), the estimated power is at least 99% at 18 months.

Amyloid PET

The null and alternative hypotheses and the statistical test are the same as those for vMRI. To estimate the sample size for the amyloid PET imaging subgroup at 18 months, a common SD of the change from baseline was estimated at 0.33 and a reasonable mean difference between treatment and placebo was estimated as 0.25 (standardized uptake value ratio [SUVR]). Assuming a moderate dose-response, the best dose would achieve a difference of 0.25 (SUVR) and the middle and low doses would achieve a difference of 0.2 and 0.15 (SUVR), respectively; this would require a total of 100 subjects from all 4 arms at 18 months to achieve 80% power.

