9.7 Statistical Methods

All statistical analyses will be performed by the sponsor or designee. Statistical analyses will be performed using SAS software or other validated statistical software as required.

All statistical tests will be based on the 5% (2-sided) level of significance, except for the Bayesian methods on the primary endpoint.

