9.7.1.6.2 SECONDARY EFFICACY ANALYSES

The MCI/Prodromal Cohort

An MMRM will be used to analyze the following secondary endpoints:

- Change from baseline in total hippocampal atrophy at 12 and 18 months of treatment in MCI/Prodromal subjects as measured by vMRI
- Change from baseline in CSF A β (1-x) after 4 weeks and 18 months of treatment in MCI/Prodromal subjects. Data from early discontinuations will also be included.

Comparisons between each treatment group and placebo will be performed.

The Mild AD Cohort

The MMRM will be used to analyze the change from baseline of derived ADCOMS at 18 months in mild AD. If there is no treatment group-by-population interaction in the overall study, the MMRM analysis will include all subjects (MCI/Prodromal or mild AD) in the overall study. Otherwise, the MMRM analysis will only include subjects in the mild AD cohort. The comparison between placebo and active doses will be performed within mild AD subjects regardless of subjects included in the MMRM analysis. Dunnett's method will be used to control for multiplicity due to multiple comparisons.

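### Hippocampal MRI and amyloid PET are powered on a 1-sided 5% Dunnett test that conflicts with the protocol's 2-sided 5% rule and is not carried into the analysis sections

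*Protocol*

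**What the plan says.** Section 9.7, repeated under Statistical Methods in the synopsis, gives the general rule: "All statistical tests will be based on the 5% (2-sided) level of significance, except for the Bayesian methods on the primary endpoint". That is the only exception named.

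Section 9.7.2.1 (and the synopsis sample-size text) describes the vMRI test for three doses against placebo: "The null hypotheses will be tested using Dunnett's method with 1-sided alpha of 0.05". The assumed reductions in hippocampal volume loss "would be 15%, 20%, and 25% corresponding to the 3 doses, respectively", and the result is: "The estimated power for the actual planned study sample size is 78% at 18 months assuming an attrition rate of 20% at 18 months". The amyloid PET paragraph adopts the vMRI hypotheses and test. It takes an SD of 0.33 SUVR and differences from placebo of 0.15, 0.20 and 0.25 SUVR, and concludes that "this would require a total of 100 subjects from all 4 arms at 18 months to achieve 80% power".

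The analysis text for MCI/Prodromal secondary endpoints (Section 9.7.1.6.2) says only: "Comparisons between each treatment group and placebo will be performed". Dunnett appears there only under the mild AD cohort. Section 9.7.1.6.3 describes the PET comparisons in the same terms, again without Dunnett. The mild AD rationale (Section 9.7.2.2) uses Dunnett at 2-sided 0.05.

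**The concern.** vMRI and PET are not the Bayesian primary analysis, so the general rule covers them and contradicts the test named in the sample-size section. That section says how the hypotheses will be tested, so it cannot be set aside as a planning assumption. The analysis sections add a third possibility, because they state neither a 1-sided level nor an adjustment for three doses.

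What is at stake is which results may be called significant. vMRI is the first-listed secondary endpoint, Section 9.2.5.4 offers it as support for disease modification, and Section 7 says the study will guide Phase 3 and is intended to be supportive for registration. If three critical values can all be defended from the text, the choice could be made after the data are seen. The printed powers also describe only one of the three tests.

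**Working it through.** **Inputs (all from the protocol).**
- General rule: 2-sided 5% (Section 9.7).
- Sizing test: Dunnett, 1-sided 0.05, three doses against placebo. The alternative is that at least one null is false, so power is the probability of rejecting at least one (Section 9.7.2.1).
- PET: SD 0.33; differences 0.15, 0.20, 0.25; 100 subjects in 4 arms, so 25 per arm; residual df 100 − 4 = 96.
- vMRI: reductions of 15%, 20%, 25%; 500 subjects with 20% attrition, so 400 completers, or 100 per arm if allocation is equal; df 400 − 4 = 396. No SD and no placebo rate of volume loss are given.

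**Method.** For each dose, T = (dose mean − placebo mean) / [s × √(1/n₀ + 1/nᵢ)], with pooled SD s, signed so that benefit is positive. The Dunnett critical value is the 95th percentile, under the null, of the largest T (1-sided) or of the largest |T| (2-sided). Both were obtained by simulation with at least one million draws.

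**Step 1: reproduce the PET figure.** Standardised effects are 0.15/0.33 = 0.455, 0.20/0.33 = 0.606 and 0.25/0.33 = 0.758. The 1-sided 0.05 Dunnett critical value is 2.09, and power at 25 per arm is 81%. The printed 80% is reproduced (24 per arm gives 79.7%), which shows that it belongs to the 1-sided test.

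**Step 2: change only the sidedness for PET.** The 2-sided 0.05 Dunnett critical value is 2.39 and power is 71%. Power is 79% at 30 per arm and just over 80% at 31 per arm (4 × 31 = 124 subjects in all).

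**Step 3: vMRI.** The 78% cannot be reproduced directly. It can be used to calibrate the missing quantity. Let k be placebo volume loss divided by its SD, so that the standardised effects are 0.15k, 0.20k and 0.25k. With 100 per arm, 1-sided Dunnett power is 78% at k = 1.436, a best-dose effect of 0.25 × 1.436 = 0.359. The same k with doubled effects gives more than 99.9%, consistent with the protocol's statement of at least 99%. With k fixed, 2-sided Dunnett gives 67%. Letting the true figure lie anywhere from 77.5% to 78.5% gives 66.8% to 68.0%, and four unequal allocations calibrated to 78% gave 67% to 68%. The doubled-effect scenario stays at about 99.9%.

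**Step 4: the third reading.** Unadjusted 2-sided 5% comparisons use t critical values of about 1.97 (df 396) and 1.98 (df 96). With the same inputs, the power to reject at least one null is about 81% for vMRI and 84% for PET.

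| Reading of the protocol | Critical value, vMRI | Critical value, PET | Power, vMRI* | Power, PET |
|---|---|---|---|---|
| Unadjusted, 2-sided 5% (9.7 with 9.7.1.6.2 and 9.7.1.6.3) | 1.97 | 1.98 | 81% | 84% |
| Dunnett, 1-sided 5% (9.7.2.1) | 2.07 | 2.09 | 78% (stated) | 81% (stated 80%) |
| Dunnett, 2-sided 5% (level from 9.7, adjustment from 9.7.2.1) | 2.36 | 2.39 | 67–68% | 71% |

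*Conditional on the stated 78%.

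For vMRI, in the direction of benefit, the three critical values correspond to nominal 2-sided p values of about 0.050, 0.040 and 0.019. A dose with t = 2.2 passes the first two and fails the third.

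**The case against.** The strongest objection is that no passage prescribes 2-sided Dunnett for vMRI or PET. Section 9.7 fixes level and sidedness, and the analysis sections name no adjustment. Read together, literally, they give unadjusted 2-sided tests, whose power exceeds the printed figures. This stands. A reader might infer that the true powers are simply 67% and 71%, but those figures require Dunnett to be kept and made 2-sided. The unadjusted reading loses no power, though it leaves three comparisons uncontrolled.

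The vMRI figure is also back-solved, and allocation will be response-adaptive. That stands too. The result barely moves with allocation, but it should not be written into a protocol as though it came from the sponsor's simulation.

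The 1-sided level looks deliberate, since both the alternative and the alpha are marked 1-sided, and listing it as a second exception in Section 9.7 would also remove the contradiction. That is true. It would, however, keep twice the error in the favourable direction that a 2-sided 5% test allows, and set a different rule from the mild AD cohort with no reason given. It would not prevent faster atrophy on drug from being estimated and reported; it would only rule out a significance claim in that direction.

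Finally, PET scanning continues until at least 25 subjects per arm have been scanned for each ligand (Section 9.2.5.3), so 100 is not a ceiling and actual PET power could be higher.

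**Conclusion.** The inconsistency is real and lies wholly in the current protocol text. For vMRI and PET, the level, the sidedness and the multiplicity adjustment are not fixed consistently, and the printed 78% and 80% hold for one of three available readings. Under 2-sided Dunnett, PET power is about 71% at 25 per arm, which rests only on the protocol's own inputs. vMRI power is about 67% to 68%, which rests on the stated 78% being right.

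Two stronger readings are not supported. One is that the sponsor's arithmetic is wrong: the PET figure reproduces under the test it names, and the vMRI figure cannot be checked. The other is that the study is undersized: the statement that "a total of 500 subjects will be sufficient" rests on the Bayesian simulations for ADCOMS, study success depends only on ADCOMS, vMRI is secondary and PET exploratory. The point should be fixed, but it does not threaten the primary conclusion.

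**What to change.** State one test for vMRI and PET, in the same terms, in Sections 9.7, 9.7.1.6.2, 9.7.1.6.3 and 9.7.2.1 and in the synopsis. The choice that fits Section 9.7 and the mild AD cohort is Dunnett's method at 2-sided 0.05 for the three dose-placebo comparisons. Then restate power: about 71% for PET at 25 per arm, or about 31 per arm if 80% is to be kept; for vMRI, a figure from the sponsor's own simulation rerun at 2-sided 0.05, giving the SD and placebo atrophy rate used. If 1-sided 5% is really intended, name it as an exception in Section 9.7, give the reason, and carry Dunnett into the analysis sections.

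The cost is wording, one rerun of an existing simulation and two less favourable power figures. No subjects or procedures are added unless the sponsor chooses to enlarge the PET subgroup. The change should be made before unblinding.

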9.7.2.2 Sample Size Rationale for the Mild AD Cohort

ADCOMS at Month 18

The null hypothesis is that there is no difference between active dose and placebo. There are 2 null hypotheses corresponding to 2 active doses. The alternative hypothesis is that at least 1 null hypothesis is false. The null hypotheses will be tested using Dunnett's test with 2-sided alpha of 0.05 as described for the mild AD cohort in [Section 9.7.1.6.2](#). The statistical power was estimated through simulation for the dose-response assumption that the percent reduction in change from baseline of ADCOMS at 18 months compared with placebo would be 33% and 50% corresponding to the 2 doses, respectively. The estimated power for the actual planned 200 mild AD subjects is at least 80% assuming a 2-sided alpha of 0.05.

9.7.3 Interim Analysis

The MCI/Prodromal Cohort

The Bayesian interim analyses and response adaptive randomization will be conducted by an unblinded external independent analysis group in accordance with the protocol. Oversight of the Bayesian interim analyses and response adaptive randomization will be conducted by an independent unblinded committee that has expertise with Bayesian adaptive design in clinical studies to ensure that the response adaptive randomization process and interim analyses perform as expected. The analysis group will provide the interim analysis outcomes to the committee at each interim analysis. The committee will ensure the integrity of the interim analysis and response adaptive randomization process through review of efficacy data. In addition, the committee will act in an independent advisory capacity to monitor the Bayesian interim analysis outcomes according to the early success and futility boundaries prespecified in the protocol. The committee will not be charged with any subject safety issues; this will remain the responsibility of the DSMB.

If the predefined early success criteria are met during the recruitment period, further recruitment and enrollment of MCI/Prodromal subjects into the study will stop (following confirmation from the Sponsor's Senior Management) and all currently randomized subjects will complete the full 18 months of treatment. No further interim analyses will be conducted after achieving early success.

If the predefined threshold for futility is reached, no additional subjects will be randomized into the study and the treatment of subjects already randomized into the study will stop and the study will be declared as "failed". All subjects will be monitored for safety for 3 months following their last dose.

If neither early success nor futility is reached and the study reaches full randomization, all subjects will complete 18 months of treatment. Interim efficacy analyses will be conducted every 3 months after full randomization is reached to assess futility and early success until all subjects complete 18 months of treatment. After full randomization, all study subjects will stop treatment only in the event of futility.

The DSMB will continue to monitor the safety aspects of the study throughout Stage A and Stage B. Details will be provided in the DSMB Charter. The study may be stopped for safety at any time.

An interim analysis will be conducted for safety when the first 60 MCI/Prodromal subjects have completed 12 weeks of treatment (or discontinue study drug early).

The first Bayesian adaptive interim analysis will be conducted when 100 MCI/Prodromal subjects have been randomized into the study (ie, 60 subjects from Stage A of the study and the first 40 subjects from Stage B of the study). Further interim efficacy analyses will be conducted after each additional 50 MCI/Prodromal subjects have been randomized, to a maximum of 500 MCI/Prodromal subjects (ie, at 100, 150, 200, 250, 300, 350, 400, 450,

500 subjects randomized). If the study reaches full randomization, additional interim analyses will be conducted every 3 months until all subjects complete 18 months of treatment. The study will be monitored for futility at each interim analysis. Starting at the interim analysis for 200 subjects, the study will be monitored for success at each interim analysis. Each interim analysis will be conducted on data for the derived ADCOMS.

In addition, at each interim efficacy analysis, response adaptive randomization will be used to update the allocation of new subjects between placebo and active doses according to a predefined automated algorithm.

The Mild AD Cohort

A group sequential design will be used for the mild AD cohort. This design includes 3 looks, 2 interim looks (when 60% and 80% information fractions are achieved) and 1 final look. The information fraction is the number of assessments in all treatment arms divided by the total number of expected assessments. Interim analyses will be performed after the MCI/Prodromal cohort crosses the early success boundary. The corresponding efficacy boundaries will be 0.076, 0.022, and 0.0423 for the first, second, and final analyses, respectively. If the actual information fraction during the interim analyses is different from 60% or 80% at the interim, the efficacy boundaries will be adjusted based on the actual information fraction.

If early success in the MCI/Prodromal cohort is not achieved before the final analysis that is performed when all subjects have completed 18 months treatment, then only a final analysis will be performed in mild AD subjects. In the event of futility in the MCI/Prodromal cohort, an analysis will be performed for the mild AD cohort based on the data for mild AD subjects available at that time.

Randomization into the Mild AD cohort will remain at a fixed schedule throughout Stage B of the study.

The interim analyses in the Mild AD cohort will be conducted by an independent analysis group.

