crosses the early success boundary. The early efficacy signal based on the change from baseline of ADCOMS at 18 months is defined as crossing the interim-analysis boundaries for overwhelming efficacy in the mild AD population. The O'Brien-Fleming (OF) boundaries based on Lan-DeMets alpha spending function will be used to assess overwhelming efficacy. The corresponding OF boundaries based on P values will be 0.076, 0.0221, and 0.0423 for the first, second, and final analyses, respectively, according to 2 planned interim analyses at the 60% and 80% information fraction.

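### The mild AD information fraction counts assessments without tying them to the month-18 ADCOMS contrast under test, so the nominal 60% and 80% looks could come before that much month-18 information exists

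*Protocol*

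**What the plan says.** Section 9.7.3 sets a group sequential design for the mild AD cohort with "2 interim looks (when 60% and 80% information fractions are achieved) and 1 final look". It then defines the fraction: "The information fraction is the number of assessments in all treatment arms divided by the total number of expected assessments". If a look falls at a different fraction, "the efficacy boundaries will be adjusted based on the actual information fraction". So one definition both times the looks and drives the boundaries.

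The quantity tested is specific to one visit. Section 9.7.1.6 says: "The early efficacy signal based on the change from baseline of ADCOMS at 18 months is defined as crossing the interim-analysis boundaries". Section 9.7.1.6.2 says: "The MMRM will be used to analyze the change from baseline of derived ADCOMS at 18 months in mild AD". Section 9.7.2.2 sizes the cohort on ADCOMS at month 18, and "The null hypotheses will be tested using Dunnett's test with 2-sided alpha of 0.05". On the spending rule, section 9.7.1.6 says: "The O'Brien-Fleming (OF) boundaries based on Lan-DeMets alpha spending function will be used to assess overwhelming efficacy".

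Table 7 schedules the ADCOMS components (ADAS-cog, MMSE, CDR) at 3, 6, 9, 12, 15 and 18 months and again at the two follow-up visits, nominally months 19 and 21.

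**The concern.** Lan-DeMets spending keeps its error rate only when the fraction fed into it measures information on the contrast being tested. A subject contributes assessments from month 3 onward but contributes a month-18 outcome only at the end. A count over all visits therefore runs ahead of month-18 information. The boundary adjustment does not repair this, because it takes the same count as input.

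Two things are at stake. O'Brien-Fleming spending is meant to release almost no alpha early, and an overstated fraction releases more. The looks are also less correlated than the boundaries assume, so the overall error rate rises above 5%. In practice the first effect matters more: a claim about 18-month change could be made when few subjects have been followed for 18 months.

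**Working it through.** **Inputs from the Protocol.** Two-sided alpha 0.05; Lan-DeMets O'Brien-Fleming spending; looks at 0.60, 0.80 and 1.00; 200 subjects; ADCOMS visits as above; Stage B at most 40 months (synopsis).

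**Assumptions.** Uniform accrual. The Protocol gives no mild AD recruitment period. The Stage B limit less about 2 months of screening, 18 of treatment and 3 of follow-up leaves 40 − 2 − 18 − 3 = 17 months. The range 9 to 30 months is shown as sensitivity; anything above 17 would overrun that limit. The 20% attrition is borrowed from the vMRI power statement in section 9.7.2.1, which concerns the MCI/Prodromal cohort. Alpha is computed for a single contrast.

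**Step 1. Reproduce the boundaries.** Cumulative spending is 4[1 − Φ(2.2414/√t)], where 2.2414 is the upper 1.25% normal point. This gives 0.0076, 0.0244 and 0.0500 at t = 0.60, 0.80 and 1.00. The nominal P values are 0.0076, 0.0221 and 0.0423. The second and third agree with the Protocol. The first does not: "The corresponding efficacy boundaries will be 0.076, 0.022, and 0.0423 for the first, second, and final analyses, respectively". That misprint is a separate error, and 0.0076 is used below.

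**Step 2. Share of subjects at month 18.** With accrual over A months, the fraction of assessments done at time T is the average over visits v of (T − v)/A, held between 0 and 1. The share at month 18 is (T − 18)/A.

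For A = 17, six visits and no dropout:
- 60% is reached at T = 20.84: (1 + 0.873 + 0.696 + 0.520 + 0.344 + 0.167)/6 = 0.600. Share = 2.84/17 = 16.7%.
- 80% is reached at T = 25.4: (1 + 1 + 0.965 + 0.788 + 0.612 + 0.435)/6 = 0.800. Share = 7.4/17 = 43.5%.

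| Accrual and visits counted | At month 18, 60% look | At month 18, 80% look |
|---|---|---|
| 9 months, six visits | 0% | 27% |
| 12 months, six visits | 2.5% | 35% |
| 17 months, six visits | 16.7% | 43.5% |
| 17 months, six visits, 20% attrition | 14.5% | 41.5% |
| 17 months, baseline also counted | 9% | 39% |
| 17 months, months 19 and 21 also counted | 33% | 62% |
| 24 months, six visits | 28.7% | 51% |
| 30 months, six visits | 35% | 56% |

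**Step 3. Month-18 information with the MMRM.** The share at month 18 is not the information, because the MMRM borrows from earlier visits. Summing the information matrices of the visits observed at each look, inverting, and taking the month-18 element relative to full data gives, for 17-month accrual (AR(1) correlation per 3 months):

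| Assumed correlation | Information at look 1 | Information at look 2 | Overall alpha |
|---|---|---|---|
| AR(1), 0.7 | 0.240 | 0.539 | 0.0590 |
| AR(1), 0.8 | 0.292 | 0.604 | 0.0573 |
| AR(1), 0.9 | 0.415 | 0.724 | 0.0537 |
| Compound symmetry, 0.5 | 0.250 | 0.563 | 0.0585 |
| Compound symmetry, 0.7 | 0.352 | 0.678 | 0.0553 |

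**Step 4. Alpha.** The last column is the probability that |Z1| ≥ 2.669, |Z2| ≥ 2.289 or |Z3| ≥ 2.031 for a trivariate normal with correlations √(ti/tj) at the true fractions. At the intended 0.60 and 0.80 the same boundaries return 0.0500. At completer-only fractions of 0.15 and 0.45 they return 0.0616.

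Early spending is the sharper contrast. The first look releases 0.0076, whereas the spending function allows about 0.00001 at t = 0.24 and about 0.001 at t = 0.415.

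**The case against.** The text does not say that every visit counts. In the definition, the word all qualifies the treatment arms; the visits are left open. With the signal, the model and the sample size all stated for month 18, a reader may take assessments to mean month-18 assessments, and then nothing is wrong. Further analytical detail is also deferred to a SAP that is not shown. This stands as far as it goes: the Protocol leaves the term undefined and does not fix an all-visits count. But the Protocol itself writes the definition, and section 9.7.1.1.3 uses the same word for clinical measurements at every visit from 12 weeks to 21 months. The literal reading is therefore a real risk.

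A reader might infer that the first look will come with 15% of subjects at month 18. The documents do not support a single figure: it depends on accrual that is not stated and on which visits are counted. A reader might also infer an overall alpha of about 6.2%. That value treats completers as the only information and ignores the MMRM.

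The gate also matters. Mild AD looks occur only after MCI/Prodromal early success, and a late gate means more mature data. If the drug does nothing in either cohort, section 9.7.2.1 puts false MCI/Prodromal success at 5% at most, so the looks would be rare. The inflation bears mainly on the case where MCI/Prodromal succeeds and mild AD is null. Finally, mild AD ADCOMS is a secondary endpoint, and no passage stops that cohort on crossing a boundary.

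**Conclusion.** The concern holds as a definition that is not tied to the tested contrast. Taken literally, it places the nominal 60% and 80% looks at roughly 0.24-0.42 and 0.54-0.72 of month-18 information, giving an overall two-sided alpha of about 5.4-5.9% instead of 5%. These figures rest on 17 months of uniform accrual, six counted visits, no dropout, the correlations listed, and looks taken as soon as the count is reached.

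The excess in alpha is modest and conditional on the gate. The larger weakness is that overwhelming efficacy at 18 months could be signalled on immature 18-month data; with 9-month accrual, nobody would have reached month 18 at the first look. The misprinted first boundary is a separate matter and adds nothing to this point.

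**What to change.** Replace the definition in section 9.7.3, and carry it into the SAP, with wording such as: the information fraction is the statistical information for the month-18 ADCOMS treatment contrast in mild AD subjects (inverse variance from the MMRM, or the number of subjects with a month-18 ADCOMS) divided by that planned. State that this fraction both times the two looks and is used to recompute the boundaries.

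On the subject count, without dropout, the looks fall at 0.60 × 200 = 120 and 0.80 × 200 = 160 subjects with a month-18 ADCOMS. Boundaries of 0.0076, 0.0221 and 0.0423 then give an overall alpha of 0.0500 at fractions of 0.60 and 0.80.

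The cost is one sentence and later looks. With 17-month accrual the first look moves from about month 21 to about month 28 after mild AD recruitment opens (18 + 0.60 × 17 = 28.2).
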